15.2.1 All adverse events

The following summaries will be provided for all adverse events (AEs):

- Summary of all AEs, screening AEs, TEAEs, including incidence and number of events;
- Summary of all TEAEs by Maximum severity;
- Summary of all study drug related TEAEs;
- Summary of all study drug related TEAEs by maximum severity.

15.2.2 Serious adverse event

The following summaries will be provided for all serious adverse events (SAEs):

- Summary of all treatment emergent SAEs;
- Summary of all study drug related treatment emergent SAEs.

15.2.3 Death

The following summaries will be provided for all deaths:

- Summary of TEAEs with an outcome of death.

15.2.4 Adverse events affecting administration of study drug or leading to study withdrawal

The following summaries will be provided:

- Summary of all TEAEs affecting administration of study drug (including dose increased, dose reduced, drug interrupted, and drug withdrawn);
- Summary of all TEAEs leading to withdrawal from study.

15.2.5 Adverse events of special interest

The following summaries will be provided for treatment-emergent adverse events of special interest:

- Serious infection
 - Summary of all treatment-emergent serious infections
 - Summary of all drug-related treatment-emergent serious infections
- Thyroid disorders (hypothyroidism, hyperthyroidism)
- Hepatic injury

15.3 CLINICAL LABORATORY EVALUATIONS

Laboratory tests include hematology, biochemistry, urinalysis, lipid profile test and thyroid function test.

The quantitative results and change from baseline will be summarized for each laboratory item at each evaluation time point. For categorical data, the number and percentage of subjects in each category will be provided.

Shift table from baseline according to normal range criteria will summarize categorical results of by visit.

Shift tables representing categorical change of laboratory results (normal and abnormal, according to normal range criteria) from baseline to each post will be provided. Shift table will also summarize categories of clinical significance from baseline to worst post-baseline value (abnormal with clinically significant > abnormal without clinically significant > normal > missing), and unscheduled visit will be included.

Line plot of the following laboratory tests over time will be provided together with its mean and 90% confidence interval by treatment group.

- Hematology: hemoglobin, absolute lymphocyte count, absolute neutrophil count, and platelet count;
- Lipid profile tests: total cholesterol, low density lipoprotein, high density lipoprotein, and triglycerides;
- Thyroid function tests: thyroid stimulating hormone (TSH), free T3 (fT3) and free T4 (fT4).

The following hepatic events will also be summarized by visit for liver chemistry:

- ALT or AST $> 8 \times$ ULN, or
- ALT or AST $> 5 \times$ ULN, or
- ALT or AST $> 3 \times$ ULN with elevated total bilirubin $> 2 \times$ ULN.

Listings of laboratory parameters will display observed values and change from baseline, if applicable, with the flag for values, which are outside of normal range. And the listings of abnormal values will be provided with flag for clinically significant abnormalities. listings containing only clinically significant laboratory values will also be provided. If there are no clinical significance evaluations, listings of abnormal values will be provided instead.

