5.3 Exclusion Criteria

Subjects presenting with any of the following criteria will not be enrolled in this study:

- 1. Subjects with historical or current evidence of clinically significant cardiovascular, neurological, psychiatric, renal, hepatic, immunological, gastrointestinal, urogenital, nervous system, musculoskeletal, skin, sensory, endocrine (including uncontrolled diabetes or thyroid disease) or hematological abnormalities that are uncontrolled. Significant is defined as any disease that, in the opinion of the Investigator, would put the safety of the subject at risk through participation, or which would affect the efficacy or safety analysis if the disease/condition exacerbated during the study
- 2. Subject has a current diagnosis of other active skin disease (e.g., psoriasis or lupus erythematosus) or skin infection (bacterial, fungal, or viral) that may affect the evaluation of atopic dermatitis
- 3. Subject has a severe comorbidity that may require systemic steroids therapy or other interventions or requires active frequent monitoring (e.g., unstable chronic asthma)
- 4. Subjects with evidence of hematopoietic disorders:
 - o Hemoglobin level < 9.0 g/dL or hematocrit < 30% at screening visit or within 3 months prior to baseline
 - Absolute white blood cell (WBC) count <3.0 x 10⁹/L (<3000/mm³) or Absolute Neutrophil Count (ANC) of <1.2 X 10⁹/L (<1200/mm³) at screening visit or within the 3 months prior to baseline.

- o Thrombocytopenia, as defined by a platelet count $<100 \times 10^9/L$ ($<100,000/mm^3$) at screening visit or within the 3 months prior to baseline.
- 5. Subjects with evidence of total bilirubin, aspartate aminotransferase (AST) or alanine aminotransferase (ALT) more than 2 times the upper limit of normal at screening visit. Patients with liver cirrhosis will be excluded.
- 6. Subjects with eGFR \leq 60 ml/min based on Cockcroft-Gault calculation (Appendix2), or patients currently undergoes regular hemodialysis
- 7. Subjects with current clinically significant infections or within 6 months of baseline (e.g., those requiring hospitalization or parenteral antimicrobial therapy or opportunistic infections), or those with a history of more than one episode of herpes zoster, a history (single episode) of disseminated zoster, a history of any infection otherwise judged by the investigator to have the potential for exacerbation by participation in the study

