5.9 Stopping Criteria

The stopping safety criteria are as follows:

- Liver chemistry threshold stopping criteria have been designed to assure subject safety and to evaluate liver event etiology (in alignment with the FDA premarketing clinical liver safety guidance). Study treatment will be stopped if the liver chemistry stopping criteria is met. Refer to Section 7.3.8 Liver Chemistry Stopping and Follow-up Criteria.
- Subject that meets the QTc criteria below will be withdrawn from the study. The QT correction formula used to determine discontinuation should be the same one used throughout the study.
 - QTc, QTcB/QTcF > 500ms
 - Change from baseline: QTc > 60ms

Withdrawal decisions are to be based on an average QTc value of triplicate ECGs. If an ECG demonstrates a prolonged QT interval, obtain 2 more ECGs over a brief period, and then use the averaged QTc values of the 3 ECGs to determine whether the subject should be discontinued from the study.

- An unacceptable adverse event, as determined by the Investigator and the medical monitor
- Any unacceptable adverse event that is thought to be related to the investigational product may result in the study being terminated
- Significant protocol deviation. The discovery that post-randomization the subject failed to meet protocol entry criteria or did not adhere to protocol requirements, and continued participation poses an unacceptable risk to the subject's health
- If the subject is found to be pregnant, the subject should be withdrawn immediately. The procedure is detailed in Section 7.3.10

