9.3.2 Other safety analyses

Observed values and actual changes from baseline of continuous laboratory parameters (hematology and biochemistry), dipstick urinalysis results evaluation (Normal, Abnormal Not Clinically Significant, or Abnormal Clinically Significant), vital signs, and ECG parameters will be summarized at each protocol scheduled time point, by actual treatment at each time point. Actual values and actual changes from baseline will be presented. Categorical outcomes will be summarized by frequency tabulations. Abnormal laboratory values will be flagged and will be identified in the listings. Microscopy data, if available, will be listed.

Shift tables representing categorical change of laboratory results from baseline to each post baseline visit will be presented. QTcF prolongation and ECG interpretations will be summarized by frequency tabulations.

Prior and concomitant medications will be coded using the World Health Organization Drug Dictionary and will be grouped by PT. The summary tables will show the number and percentage of subjects by PT, for all subjects overall. Prior medications are those medications that were stopped prior to first study treatment. Concomitant medications are medications taken at least once after first study treatment. Medications stopped on the same day as first study treatment will be considered as prior medication only. Only concomitant medications will be summarized. Prior medications will be listed only. Prior and concomitant medications will be listed separately. For the summaries of concomitant medications, subjects who take the same medication (in terms of the PT) more than once will only be counted once for that medication.

Physical examination and pregnancy data will be listed only.

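### The laboratory shift tables in SAP 15.3 pool low and high values, and outside adverse event reporting no planned table counts subjects per arm whose blood counts went low

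*SAP*

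**What the plan says.** SAP 15.3 describes three laboratory shift displays.

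- A normal-range shift by visit, with no categories listed: "Shift table from baseline according to normal range criteria will summarize categorical results of by visit".
- A normal-range shift with its categories in brackets: "Shift tables representing categorical change of laboratory results (normal and abnormal, according to normal range criteria".
- A shift on the investigator's judgement: "Shift table will also summarize categories of clinical significance from baseline to worst post-baseline value". This one includes unscheduled visits.

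Protocol 9.3.2 leaves the categories open: "Shift tables representing categorical change of laboratory results from baseline to each post baseline visit will be presented".

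SAP 15.3 also summarises values and changes: "The quantitative results and change from baseline will be summarized for each laboratory item at each evaluation time point". It plots means with 90% confidence intervals for haemoglobin, lymphocytes, neutrophils, platelets, lipids, TSH, fT3 and fT4, and it lists individual values with out-of-range flags. Its threshold table covers ALT, AST and bilirubin only.

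On entry, Protocol 5.3 item 4 excludes on low counts: "Hemoglobin level < 9.0 g/dL or hematocrit < 30% at screening visit or within 3 months prior to baseline", WBC below 3.0, neutrophils below 1.2 or platelets below 100 (each x 10^9/L). Item 18 excludes subjects with abnormal TSH, fT4 or fT3 at screening. Among the events of special interest, SAP 15.2.5 names "Thyroid disorders (hypothyroidism, hyperthyroidism".

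**The concern.** Laboratory parameters, lipids and thyroid function are listed safety endpoints under a secondary objective, and for several of them direction carries the meaning. Hypothyroidism and hyperthyroidism pull TSH opposite ways. The haematology entry limits concern low counts only. A shift table that records only whether a value is inside or outside the range cannot say which way subjects moved. It also cannot register a further fall in someone who was already below the range at baseline.

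At stake is whether a reader of the study report can answer a plain question: how many subjects on each dose, and on placebo, had counts that went low? The SAP answers the equivalent question for liver tests (15.3) and for QTc (15.5), but not for blood counts.

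**Working it through.** The documents give no figure to reproduce here. The check is on what the table categories can and cannot distinguish.

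**1. Loss of direction.** Take 35 subjects (the group size in SAP 6; the argument does not depend on it) and assume three patterns of low (L), normal (N) and high (H) values. The counts are invented for illustration.

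| Pattern | Three-level shifts | Two-level table as in SAP 15.3 | Newly low |
|---|---|---|---|
| A | N→L 6, N→N 25, L→L 4 | normal→abnormal 6, normal→normal 25, abnormal→abnormal 4 | 6/35 = 17.1% |
| B | N→H 6, N→N 25, L→L 4 | the same | 0/35 = 0% |
| C | N→L 3, N→H 3, N→N 25, L→H 4 | the same | 3/35 = 8.6% |

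If one arm followed A and another followed B, the SAP table would show 6/35 = 17.1% normal-to-abnormal in both. A directional table would show 17.1% against 0% newly low.

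**2. Low baseline.** Entry is permitted from the exclusion limit upwards, so the affected band runs from that limit to the lower limit of normal (LLN). The documents give no reference ranges; the LLN ranges below are assumptions.

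| Test | Entry limit | Assumed LLN | Width of band |
|---|---|---|---|
| Haemoglobin (g/dL) | 9.0 | 11 to 13 | 11 − 9 = 2 to 13 − 9 = 4 |
| Neutrophils (x 10^9/L) | 1.2 | 1.5 to 2.0 | 0.3 to 0.8 |
| Platelets (x 10^9/L) | 100 | 125 to 150 | 25 to 50 |

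A subject whose baseline is in the band is abnormal at baseline, and any further fall is recorded as abnormal-to-abnormal. The same holds for WBC if its LLN is above 3.0 x 10^9/L. How many subjects enter in these bands cannot be known from the documents.

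**3. What the other displays supply.**

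| Display | Direction kept? | Count of subjects per arm? |
|---|---|---|
| Per-visit values and changes (SAP 15.3, statistics from 10.1 including minimum and maximum) | Yes | No; shows the extreme value only |
| Line plots of means | Yes | No |
| Flagged listings | Yes, from the values listed | No |
| Clinical-significance shift to worst value | No | Yes, but by investigator judgement |
| Threshold table | Yes | Liver chemistry only |
| Adverse event tables | Where the coded term carries it | Only for findings reported as adverse events |

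SAP 11.3 adds a further limit. Where a scheduled value exists, it takes precedence over an unscheduled one, and multiple results at a timepoint are averaged. A low value at an unscheduled visit can therefore be absent from the by-visit tables.

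**The case against.** The strongest reply is that the information is largely available elsewhere. Under SAP 10.1 every continuous summary carries the minimum and maximum, so each visit's table shows the lowest neutrophil count and the largest fall in each arm, whatever the baseline category. Listings show individual values with flags. A low count reported as an adverse event is coded to a preferred term and tabulated by arm. A worsening low count can move from not clinically significant to clinically significant in the worst-value shift. Table shells are in a separate document, and one normal-range shift sentence in 15.3 lists no categories, so the final layout may be better than the text suggests.

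All of this stands, and it limits the point. It does not supply the missing count: a minimum describes one subject, a listing is not a tabulation by arm, and the significance shift and adverse event reporting both rest on judgement. Where the SAP does name categories, it names two.

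A reader might infer more than the documents support:

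- **That rises and falls cancel.** They are added together in one cell; nothing is subtracted.
- **That the normal/abnormal table is the only laboratory shift, or that an effect would be hidden.** The displays above remain, so the effect is obscured in this table rather than lost.
- **That the documents name cytopenia as a drug risk.** Protocol 5.3 item 4 is an eligibility rule, and the special-interest list is serious infection, thyroid disorders and hepatic injury. The text of Protocol 2.4 is not in the available copy, so this cannot be confirmed either way.
- **That the low-baseline problem extends to thyroid tests.** Abnormal thyroid values at screening are excluded, so only the loss of direction applies there. The special-interest summary and the plots keep some of that direction.

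It is also fair to say that low/normal/high alone does not solve the low-baseline problem, because a further fall would still read low-to-low.

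**Conclusion.** The point holds as a reporting weakness of minor to moderate weight. The two-level normal-range shift table pools low and high values and cannot show a further fall from a permitted low baseline. The only laboratory shift to a worst value is judgement-based and has no direction. Apart from adverse event reporting, no planned table counts subjects per arm whose blood counts went low.

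The pooling follows directly from the wording of SAP 15.3. The low-baseline part rests on the assumption that the lower limits of normal exceed the entry limits in Protocol 5.3. The conclusion as a whole is subject to what the unseen table shells contain. The primary result, the hypothesis tests and data collection are not affected.

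**What to change.** In SAP 15.3 and the table shells:

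1. Replace normal/abnormal with low/normal/high for each quantitative test. Tabulate the shift by visit, and separately from baseline to the lowest and to the highest post-baseline value, with unscheduled values included in those two.
2. Add a descriptive count per arm of subjects with any post-baseline value below the protocol's own entry limits: haemoglobin < 9.0 g/dL, WBC < 3.0 x 10^9/L, neutrophils < 1.2 x 10^9/L, platelets < 100 x 10^9/L. State that these are reporting thresholds taken from Protocol 5.3 and not clinical rules.

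The second item is needed because the first leaves a further fall as low-to-low. Even so, the count misses a fall that stays above the limit (haemoglobin from 11 to 9.2 g/dL, for example); for those, the per-visit minimum change and the listings remain.

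Protocol 9.3.2 does not fix the shift categories, so the change does not conflict with it. No new data are required. The cost is SAP wording, revised shells and slightly larger tables.

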7.3.8 Liver Biochemistry – Stopping and Follow-up Criteria

Phase II Liver Biochemistry Stopping and Follow-up Criteria have been designed to ensure subject safety and to assess liver event etiology (consistent with FDA premarketing clinical liver safety guidance). If any of the following conditions occur at any time during the study drug treatment period, the study drug should be discontinued immediately with appropriate clinical follow-up (including repeat laboratory tests until the subject's laboratory values return to normal or return to baseline condition):

- ALT or AST > 8 x ULN, or
- ALT or AST > 5 x ULN and retest 5 x ULN, or
- ALT or AST > 3 x ULN with elevated total bilirubin > 2 x ULN, or international normalized ratio > 1.5, or
- ALT or AST > 3 x ULN associated with fatigue, nausea, vomiting, right upper quadrant pain or tenderness, fever, rash.

For one of above criteria, make every effort to carry out the liver event follow-up assessment of described below:

- Viral hepatitis serology including:
 - Hepatitis A IgM antibody;
 - Hepatitis B surface antigen and Hepatitis B core antibody (IgM);
 - Hepatitis C virus RNA;
 - Cytomegalovirus IgM antibody;
 - Epstein-Barr viral capsid antigen IgM antibody (if not available, obtain heterophile antibody or monospot testing);
 - Hepatitis E IgM antibody
- Blood sample for pharmacokinetic (PK) analysis, obtained within 24 hours of last dose. Record the date/time of the PK blood sample draw and the date/time of the last dose of investigational product prior to blood sample draw on the eCRF. If the date or time of the last dose is unclear, provide the subject's best approximation. If the date/time of the last dose cannot be approximated OR a PK sample cannot be collected in the time period indicated above, do not obtain a PK sample. Instructions for sample handling and shipping are in the SPM.
- Serum creatine phosphokinase (CPK) and lactate dehydrogenase (LDH)

- Fractionate bilirubin, if total bilirubin≥2xULN
- Obtain complete blood count with differential to assess eosinophilia
- Record the appearance or worsening of clinical symptoms of hepatitis, or hypersensitivity, such as fatigue, nausea, vomiting, right upper quadrant pain or tenderness, fever rash or eosinophilia as relevant on the AE report form
- Record use of concomitant medications, acetaminophen, herbal remedies, other over the counter medications, or putative hepatotoxins, on the concomitant medications report form

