11.3 MULTIPLE MEASUREMENTS AT THE SAME TIMEPOINT

If there are multiple measurement results at a timepoint, unless otherwise specified, use the mean of these measurements to summarize and derive. If there is unscheduled measurement, consider the

scheduled data firstly, if missing at the scheduled visit, then impute with closest non-missing per-protocol data within the visit window to make analysis.

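### The liver-criteria table in SAP 15.3 is by visit only, so a criterion met only at an unscheduled test is not counted by arm

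*SAP*

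**What the plan says.** **SAP 15.3** lists three liver thresholds: ALT or AST above 8 times ULN, above 5 times ULN, and above 3 times ULN with total bilirubin above 2 times ULN. The only tabulation is introduced by "The following hepatic events will also be summarized by visit for liver chemistry". No row for any time after baseline is specified. The same section plans a shift table to the worst post-baseline value, for which it adds "and unscheduled visit will be included". That table uses clinical-significance categories, not multiples of ULN.

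**SAP 11.3** sets the general rule. Scheduled data come first. For unscheduled data the rule is "if missing at the scheduled visit, then impute with closest non-missing per-protocol data within the visit window". Where a timepoint has several results, the default is to "use the mean of these measurements to summarize and derive".

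**Protocol 7.3.8** is not tied to visits: "If any of the following conditions occur at any time during the study drug treatment period, the study drug should be discontinued immediately". The follow-up it requires is described as "including repeat laboratory tests until the subject's laboratory values return to normal or return to baseline condition". One of its criteria depends on a second test: "ALT or AST > 5 x ULN and retest 5 x ULN". It also has INR and symptom elements that the SAP list lacks.

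**The concern.** The protocol acts on liver values whenever they occur and generates tests between visits, through repeat testing and through extra safety samples at the investigator's discretion (protocol 7.3.5, Clinical Laboratory Testing). The SAP counts the thresholds only in visit rows. Where the SAP's authors wanted worst values with unscheduled results included, in the clinical-significance shift table, they said so. The liver table has no such statement.

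What is at stake is the completeness of the by-arm liver count. Liver function is a named safety endpoint (SAP 3.2.2.1) and hepatic injury is an event of special interest (SAP 15.2.5). A subject could meet a listed threshold between visits and appear in no row of the table meant to count such subjects.

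**Working it through.** The plan states no figure to reproduce. The check sets the rules side by side, counts the days they leave uncovered, and runs example subjects through both ways of counting.

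**1. Which tests can enter a by-visit row.** Combining SAP 15.3 with SAP 11.3:
- a scheduled result enters;
- an unscheduled result inside a window enters only if the scheduled result is missing;
- an unscheduled result outside every window does not enter;
- several results at one timepoint are averaged, which can pull a value above a threshold to below it.

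**2. How much of the study lies outside the windows.** Protocol Table 1 gives 7±2, 28±3, 56±3, 84±3 and 98±3 days, that is Days 5–9, 25–31, 53–59, 81–87 and 95–101.
- Days 1–84: the gaps are 1–4, 10–24, 32–52 and 60–80. 4 + 15 + 21 + 21 = 61 days; 61/84 = 73%.
- Days 1–98: add Days 88–94, so 61 + 7 = 68 days; 68/98 = 69%.

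These are calendar days, not a share of tests or cases. Table 1 also places the early-withdrawal visit in the Visit 7 column, so results from that visit may reach a row even when drawn outside Days 95–101. The SAP does not say.

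**3. Example subjects (assumed values, multiples of ULN, not trial data).**

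| Subject | ALT results | By visit, scheduled only | Any time, unscheduled included |
|---|---|---|---|
| A | 2.5 at Day 28; 6.0 unscheduled at Day 40; 2.0 at Day 56 | no criterion met | above 5 |
| B | 5.5 at Day 28; 9.0 unscheduled at Day 32; 1.5 at Day 56 | above 5 only | above 5 and above 8 |
| D | 5.6 at Day 28; 5.4 unscheduled at Day 31 | above 5 | above 5 |

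A is lost altogether, B is placed in too low a category, and D is counted either way. The same logic applies to the combined criterion when the bilirubin rise is seen only off schedule.

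**4. Whether another output supplies the count.**
- Listings (SAP 10.2 and 15.3) show unscheduled values but give no rate by arm.
- The worst-value shift table includes unscheduled visits but cannot separate 3, 5 and 8 times ULN.
- The hepatic-injury summary (SAP 15.2.5) depends on a reported adverse event and has no laboratory definition.
- Protocol 7.3.12(g) makes possible drug-induced liver injury with ALT at least 3 times and bilirubin at least 2 times ULN an SAE. SAEs are summarized (SAP 15.2.2), but that rule names ALT, not AST, and does not cover isolated rises above 5 or 8 times ULN.

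None is a count by arm against the thresholds.

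**5. Weight of one subject.** With the SAP's 35 per arm, 1/35 = 2.9% of an arm and 1/70 = 1.4% of the two active arms together. With the protocol's 44 per arm, 1/44 = 2.3%. For the pooled 70, the one-sided 95% upper bound is 1 − 0.05^(1/70) = 4.2% for no cases. For one case, solving (1 − p)^70 + 70p(1 − p)^69 = 0.05 gives 6.6%.

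**6. The two lists of criteria.**

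| Element in protocol 7.3.8 | SAP 15.3 |
|---|---|
| above 8 times ULN | same |
| above 5 times ULN with retest | above 5 times ULN, no retest |
| above 3 times ULN with bilirubin above 2 times ULN | same |
| INR alternative to bilirubin | absent |
| above 3 times ULN with symptoms | absent |

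**The case against.** SAP 15.3 does not itself say that unscheduled results are left out, and the table shells are in a separate document (SAP 17.2). That stands: the exclusion follows from the by-visit wording read with SAP 11.3, and shells could depart from it. The plan as written, however, contains no any-time count.

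A subject above 5 times ULN at a scheduled draw is counted whatever the retest shows. This also stands. Omitting the retest makes the SAP's criterion more inclusive than the protocol's, so the loss is confined to a first crossing, a step up in category, or a bilirubin rise seen only off schedule. No figure in the documents shows how often that happens.

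Three stronger readings are tempting and are not supported:
- **That ALT and bilirubin peaks at different visits are wrongly left out.** Both documents ask for the ALT or AST rise together with the bilirubin rise, most naturally a concurrent finding, and neither pairs maxima across visits. An example with ALT 4 times ULN at Week 4 and bilirubin 2.4 times ULN at Week 8 is not a missed case under that wording. Pairing unrestricted maxima could join unrelated rises.
- **That combined cases vanish from the safety results.** Protocol 7.3.12(g) should bring a combined ALT case in as an SAE.
- **That one missed case changes the safety conclusion.** Protocol 9.3 makes safety descriptive, with no threshold or decision rule. The pooled upper bound moves from 4.2% to 6.6%.

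The absent INR element is also not a simple oversight in tabulation. INR is not on the laboratory panel (protocol Table 6), and 7.3.12(g) says measuring it is not required.

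**Conclusion.** The point holds for the liver table. As written, SAP 15.3 with SAP 11.3 does not count a listed criterion that is first met, or a higher category that is reached, only at an off-schedule test, while protocol 7.3.8 applies at any time and requires such tests. The cases can surface elsewhere, but not as a count by arm against the thresholds.

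The number of affected subjects cannot be derived from the documents. Each would change the reported rate in an arm by 2.9 percentage points at 35 per arm. This is a worthwhile reporting correction, not a threat to a formal conclusion.

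It assumes that SAP 11.3 governs the liver table and that the unseen shells add no any-time row.

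**What to change.** Add to SAP 15.3 a table by arm with the number and percentage of subjects meeting each listed criterion at any time after baseline. Include unscheduled results, and use individual results, not the SAP 11.3 average. Keep the by-visit table.

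For the combined criterion, count ALT or AST and bilirubin elevations on the same date or within a window that the SAP states. A plot of maximum ALT against maximum bilirubin can be added as a descriptive supplement only, because its maxima may come from different dates.

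Reconcile the SAP list with protocol 7.3.8 on the retest, INR and symptom elements. State that INR is not routinely collected, and that symptoms are recorded on the AE form, so counts on those elements would need more than the laboratory data.

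The cost is one table and one figure from laboratory data already collected, plus a short text change settled before unblinding.
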